4.2 END OF STUDY DEFINITION

The participant is considered to have completed the study if they have completed all the listed study procedures in the Schedule of Activities (SoA), Section 1.2. The end of this study is defined as completion of the last visit or procedure shown in the SoA in the trial globally.

5. STUDY POPULATION

5.1 INCLUSION CRITERIA

In order to be eligible to participate in this study, an individual must meet the following criteria:

- Age 21-45
- Meeting NIAAA criteria for current at-risk drinking (i.e., >7/14 drinks in one week for women/men, with at least one episodes of 4+/5+ drinks in the past 30 days)
- Willingness to complete laboratory sessions involving blood draws and alcohol administration
- Ability to communicate and read in English
- Body mass index (BMI) of 18.5 - 30 kg/m²
- Own an iPhone with Apple iOS 6 or higher compatible with the Skyn app

5.2 EXCLUSION CRITERIA

An individual who meets any of the following criteria will be excluded from participation in this study.

- Meets past-year criteria for severe AUD (>7 of 11 symptoms endorsed) or AUDIT score of 20+
- Meeting past-year criteria for a substance use disorder (with the exception of alcohol, tobacco or mild cannabis use disorder)
- Current engagement in alcohol treatments, or currently engaged in intentional efforts to quit alcohol use
- Current use of GLP-1 receptor agonist medication or weight control medications
- Lifetime diagnosis of severe mental illness (including schizophrenia and bipolar disorder)
- History of suicide attempt, or recent (past 30 day) suicidal ideation, or psychiatric hospitalization in the last 6 months
- History of diabetes
- Medical conditions or medications for which alcohol is contraindicated

- Pregnant, nursing, or trying to become pregnant
- Plans to travel during the duration of study participation

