1.2 SCHEDULE OF ACTIVITIES (SOA)

Procedures	Online Prescreen	Virtual Visit	Study visit 1	Study Visit 2	7 day Remote Assessment	Discharge visit
Online prescreen survey	X					
Informed consent		X				
DSM-5 SCID AUD and SUD		X				
Demographics Form		X				
Alcohol Use Identification Test (AUDIT)		X				
Inventory of Drinking Situations (IDS)		X				
Obsessive Compulsive Drinking Scale (OCDS)		X				
Reward-based Eating Drive Scale (RBEDS)		X				
Body Perception Questionnaire (BPQ)		X				
Drinking Motives Questionnaire (DMQ)		X				
Comprehensive Relative Autonomy Index for Drinking (CRAI Drinking)		X				
Alcohol Sensitivity Questionnaire (ASQ)		X				
Impaired Control Scale (ICS)		X				
Dietary supplement or placebo			X	X		
Administer alcohol priming drink			X	X		
Paced alcohol or control drinking			X	X		
Weight and height			X			
Pregnancy test			X	X		
Alcohol-specific satiety questionnaire			X	X		
Drug Effects Questionnaire (DEQ)			X	X	X	
Visual Analogue Scale (VAS)			X	X		
Biphasic Alcohol Effects Scale (BAES)			X	X		
Subjective Effects of Alcohol Scale (SEAS)			X	X		
Alcohol Urge Questionnaire (AUQ)			X	X		
Alcohol Purchase Task (APT)			X	X		
Dot Probe task			X	X		
Breath Alcohol Concentration (BrAC)			X	X	X	
Transdermal Alcohol Concentration (TAC), measured via Skyn			X	X	X	
Ecological Momentary Assessment (EMA)					X	
DEXA scan					X	
Venipuncture blood sample x2			X	X		
Fingerprick blood sample x3			X	X		
Timeline followback (TLFB)						X
Brief young adult alcohol consequences questionnaire						X
Importance of consequences of drinking short-form						X
Return Skyn monitor						X

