Risk from Participation in Alcohol Administration Sessions: Other potential risks include typical risks related to participation in alcohol administration studies. For example, it is possible that participants may experience dizziness/nausea from drinking during these visits, or symptoms the following day (e.g., headache). Our group has considerable experience with alcohol administration procedures [80-84], and the safety precautions required in these studies. Across these studies, the incidence of adverse events such as vomiting has been exceptionally low. Our procedures will follow the NIAAA recommended guidelines for administering alcohol to human subjects (<https://www.niaaa.nih.gov/Resources/ResearchResources/job22.htm>). Briefly, the NIAAA guidelines include recommendations for administering alcohol to participants who meet criteria for AUD. In particular, we have taken measures to protect against ethical concerns by *excluding treatment-seekers* (or those engaged in an active quit attempt), as per the NIAAA recommended guidelines. Additionally, we will screen out participants with severe AUD (defined as 6 or more of 11 symptoms). This approach allows us to generate data relevant to a clinical population while minimizing risks.

Risk from Dietary supplements: There is the infrequent and mild potential risk of gastrointestinal discomfort associated with dietary fiber and green tea extract supplements. To minimize these risks, effective doses of each supplement have been chosen which have been shown to be safe and tolerable for human subject research in prior studies [52, 53].

Risk from blood draws: There is a rare (<1%) risk of infection following blood draws. Trained personnel will conduct all procedures and the site of blood draws will be cleaned appropriately prior to data collection.

Potential physical risks: During the dual x-ray absorptiometry scan (DEXA) subjects will be exposed to very low doses of radiation. The amount of x-ray radiation that subjects will receive during the scan is approximately 0.8 mrems, which is extremely small. The amount of radiation is less than one tenth of the amount used during a normal chest X-ray and significantly less than the radiation received from natural background in a year (300 mrem).

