4.2 PARTICIPANTS

We will aim to recruit 42 adults who meet NIAAA criteria for at-risk drinking; >7/14 standard drinks per week for women/men, with at least one past-month heavy drinking episode defined as 4/5+ standard drinks for women/men. To ensure a range of alcohol use in the sample we will aim to recruit an even number of participants from AUDIT zones 1, 2 and 3 (AUDIT total score = 0-7, 8-15, and 16-19 respectively) which reflect different levels of alcohol use health risk severity [57]. The AUDIT is a validated screening tool that indexes alcohol use severity, but is not a diagnostic instrument. Typically an AUDIT score of 20 or greater indexes elevated risk for alcohol use disorder; those with scores of 20+ will be excluded. In addition, we will aim to recruit an even distribution of males and females across AUDIT zones. Participants will be recruited via flyers and social media ads from the triangle area (Chapel Hill, Raleigh, Durham). Interested participants will fill out an online pre-screen survey using Research Electronic Data Capture (REDCap) to determine initial eligibility. We estimate screening 250 people will yield 55 eligible participants to consent. Accounting for study drop-outs, we expect that 55 consents will allow for a final sample size of 42 who complete all study procedures, which is a feasible goal for the 12-month study. Potentially eligible participants will be contacted via email to schedule a virtual visit including additional screening and informed consent. A research assistant will explain the study requirements and both parties will sign the consent documents via REDCap if agreeing to enroll in the study. The DSM-5 SCID will then be administered to screen for alcohol and substance use disorder.

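### Sections 2.3.1 and 5.2 contradict each other on the severe-AUD exclusion: a person with 6 or 7 of 11 symptoms and an AUDIT score of 19 or below is screened out by one and eligible under the other

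*Combined protocol and SAP*

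**What the plan says.** Two places in the protocol define the severe-AUD exclusion by number of symptoms.

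- **Section 2.3.1 (Known Potential Risks)**, in the paragraph on alcohol administration sessions: "we will screen out participants with severe AUD (defined as 6 or more of 11 symptoms". The paragraph offers this as one of the measures that keep risk down while still allowing people who meet AUD criteria to be studied.
- **Section 5.2 (Exclusion Criteria)**, first item: "Meets past-year criteria for severe AUD (>7 of 11 symptoms endorsed) or AUDIT score of 20", followed by a plus sign. A person is excluded on either limb, the symptom count or the AUDIT score.

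The other relevant text gives no symptom count.

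- **Section 4.2 (Participants)**: "The DSM-5 SCID will then be administered to screen for alcohol and substance use disorder". On the AUDIT it agrees with Section 5.2: "those with scores of 20+ will be excluded". It plans even recruitment from three zones, "AUDIT total score = 0-7, 8-15, and 16-19 respectively".
- **Section 1.2 (Schedule of Activities)** lists "DSM-5 SCID AUD and SUD" once, at the virtual visit.
- **Section 5.2**, second item, exempts alcohol from the general substance use disorder exclusion: "Meeting past-year criteria for a substance use disorder (with the exception of alcohol, tobacco or mild cannabis use disorder".

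**The concern.** The same term, severe AUD, carries two different cut-offs. Section 5.2 is the list that screening staff would be expected to apply. Section 2.3.1 describes the protection that readers of the risk assessment are told is in place. Applying Section 5.2 as written does not deliver that protection for people given alcohol in the laboratory.

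The conflict acts at the virtual visit, before any dosing, but its effects can run further. Sections 6.1 and 6.2 make meeting an exclusion criterion a reason to stop or withdraw a participant, and Section 6.2 replaces participants who consent but do not complete. Deviation recording (Sections 9.1.7.1 and 9.1.10) also lacks a single standard: enrolling someone with 6 symptoms complies with Section 5.2 and departs from Section 2.3.1. Section 9.1.7 says there is no site monitoring plan, so noticing the discrepancy rests on the study team's own review.

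**Working it through.** The plan gives no figure to reproduce. The check lists every possible symptom count and compares the two rules.

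**Inputs**

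- Symptom count *k*: an integer from 0 to 11 (both sections count out of 11).
- Section 2.3.1 rule: exclude if *k* ≥ 6.
- Section 5.2 rule: exclude if *k* > 7, or if AUDIT ≥ 20.
- AUDIT ≥ 20 is treated as excluded throughout, because Section 4.2 (Participants) says so as well.

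**Symptom limb alone**

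- Section 2.3.1 excludes {6, 7, 8, 9, 10, 11}.
- Section 5.2 excludes {8, 9, 10, 11}.
- Difference: {6, 7}.

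**With the AUDIT limb added**

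At AUDIT 20 or above, everyone is excluded and the conflict disappears. At AUDIT 0 to 19 the AUDIT limb is silent and the result depends on the count:

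| Symptoms | Section 2.3.1 | Section 5.2 as written | Section 5.2 read as 7 or more |
|---|---|---|---|
| 0–5 | not excluded | not excluded | not excluded |
| 6 | excluded | **not excluded** | **not excluded** |
| 7 | excluded | **not excluded** | excluded |
| 8–11 | excluded | excluded | excluded |

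Bold marks disagreement with Section 2.3.1. The last column allows for the sign being a slip, or a greater-than-or-equal sign lost in text extraction. It leaves {6, …, 11} minus {7, …, 11} = {6}, so some conflict remains on either reading.

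**Could other text settle it?**

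- The AUDIT limb cannot. The three recruitment zones run from 0 to 19, so everyone the study intends to enrol lies in the range where only the symptom limb of this criterion can exclude. Section 4.2 also says the AUDIT is not diagnostic.
- The substance use disorder exclusion cannot, because it exempts alcohol.
- Section 4.2 and the schedule say when and with what instrument AUD is assessed, but not which count fails.
- The remaining exclusions, such as treatment engagement, attempts to quit and medical contraindications, do not depend on the AUD symptom count. A given person with 6 or 7 symptoms might be caught by one of them, but not because of that count.

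**The case against.** The best counter-argument is that Section 5.2 excludes people who meet criteria for severe AUD, with the count only in parentheses. The one other definition of that term in the protocol is the count in Section 2.3.1. A screener could let the words govern, treat the parenthesis as a slip and exclude at 6. The two rules can also both be obeyed: an exclusion list does not oblige anyone to enrol a person, and staff applying both texts would simply use the stricter one.

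That reading is possible, and it means no one is required to be dosed contrary to Section 2.3.1. It does not remove the conflict. The parenthesis is the only symptom cut-off in the formal criteria, and a screener who follows it passes people whom the risk section says are screened out.

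Several points on size stand. Only counts of 6 and 7 are affected, and only 6 is certain whichever way the sign is read. The number of people may be small or zero. Section 2.3.1 accepts dosing people who meet AUD criteria. Other safeguards apply at every count: the exclusions for treatment-seeking and for contraindications, the planned maximum BAC, and staying in the laboratory until BAC is zero. The symptom count enters no planned analysis; the aim 3 model uses AUDIT as a continuous predictor. The case therefore rests on participant protection and a clear eligibility rule, not on power or bias.

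A smaller point also stands: Section 5.2 specifies the past year and Section 2.3.1 gives no time window, so aligning the count alone would leave the two texts different.

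**Conclusion.** The plan is wrong as written and must be corrected. For a person with 6 or 7 symptoms, AUDIT 0 to 19 and no other reason for exclusion, Section 2.3.1 says screened out and Section 5.2 says eligible. If Section 5.2 meant 7 or more, the contradiction narrows to exactly 6 but does not vanish.

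The result assumes only that symptom counts are whole numbers and that AUDIT 20 or above is always excluded. How many participants it touches cannot be derived from the documents. The IRB application and standard operating procedures, which Sections 9.1.7.1 and 9.1.8 say will be followed, are not among the documents, so the count that staff actually apply is unknown. The severity comes from what the criterion controls, which is access to alcohol dosing under a protection the protocol says it provides.

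**What to change.** Reconcile Sections 2.3.1 and 5.2 so that both state one symptom count in the same form (N or more of 11) and over the same time window. The choice of N belongs to the investigators and the IRB; none is proposed here.

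Then:

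- put the same count on whatever form staff use to record the SCID eligibility result (the protocol does not name one);
- give the count, or a cross-reference to Section 5.2, in the SCID sentence of Section 4.2 (Participants);
- check that the risk paragraph in Section 2.3.1 describes the population that will actually be enrolled;
- submit the correction to the IRB.

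The cost is a short text correction, one matching line on the screening record and an IRB submission. Any change in screen failures depends on the count chosen and cannot be estimated from the documents.

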5.3 SCREEN FAILURES

The prescreen procedures should identify most participants who will become screen failures if consented to participate. The online prescreen and phone screen assess all previously stated eligibility and exclusion criteria except 1) SUD and psychiatric disorders 2) current use of prescription psychoactive medication 3) pregnancy. There is still a chance that the first session reveals that they do not meet study criteria. The study personnel completing the interviewing process will notify participants of their ineligibility.

5.4 STRATEGIES FOR RECRUITMENT AND RETENTION

This study will utilize multiple recruitment strategies to communicate this opportunity to as many potential participants as possible. We estimate that approximately 55 participants will be enrolled from the Triangle area. Potential participants will be informed of the study through email and listserv announcements with study information or a flyer/ brochure with a link to the prescreen survey on REDCap. Potential participants may also find study information through advertisements with a link to the prescreen survey on UNC research for me, social media (Facebook/Twitter/Instagram), and craigslist.com (in the gigs section). Interested individuals can then complete the prescreen survey, which will indicate whether they consent to be contacted about the study. Monetary incentives will be used for study retention as described in Section 4.1.

6. DISCONTINUATION OF STUDY / PARTICIPANT DISCONTINUATION/WITHDRAWAL

6.1 DISCONTINUATION OF STUDY INTERVENTION

Discontinuation of the study means that study participation is halted and study procedures are not completed. The study procedures will be discontinued for the following reasons:

- Any unanticipated problem, laboratory abnormality, intercurrent illness or other medical condition, or situation occurs such that continued participation in the study would not be in the best interest of the participant.
- The participant meets any exclusion criteria (either newly developed or not previously recognized).

6.2 PARTICIPANT DISCONTINUATION/WITHDRAWAL FROM THE STUDY

Participants are free to withdraw from participation in the study at any time upon request.

An investigator may discontinue or withdraw a participant from the study for the following reasons:

- Any unanticipated problem or other medical condition or situation occurs such that continued participation in the study would not be in the best interest of the participant.

- The participant meets any exclusion criteria (either newly developed or not previously recognized).
- The participant cannot complete study procedures or attend sessions as required.

The reason for participant discontinuation or withdrawal from the study will be recorded with the participant files. Participants who sign the informed consent form but do not fully complete study procedures will be replaced.

6.3 LOST TO FOLLOW-UP

A participant will be considered lost to follow-up if he or she fails to attend Study Day 2 and is unable to be contacted by the study site staff. All efforts will be made to ensure participants are not lost to follow-up, including developing rapport and ensuring enrolled participants are reminded of their session dates. Every effort will be made to contact participants who are lost to follow-up, including contacting via email and phone. Any participant that is lost to follow-up will be replaced.

7. UNANTICIPATED PROBLEMS

7.1 DEFINITION OF UNANTICIPATED PROBLEMS (UP)

The Office for Human Research Protections (OHRP) considers unanticipated problems involving risks to participants or others to include, in general, any incident, experience, or outcome that meets all of the following criteria:

- Unexpected in terms of nature, severity, or frequency given (a) the research procedures that are described in the protocol-related documents, such as the Institutional Review Board (IRB)-approved research protocol and informed consent document; and (b) the characteristics of the participant population being studied;
- Related or possibly related to participation in the research (“possibly related” means there is a reasonable possibility that the incident, experience, or outcome may have been caused by the procedures involved in the research); and
- Suggests that the research places participants or others at a greater risk of harm (including physical, psychological, economic, or social harm) than was previously known or recognized.

7.2 UNANTICIPATED PROBLEM REPORTING

If an UP occurs, the IRB will be notified, and the study will be adjusted as needed to protect the health and safety of the participants. Depending on the nature of the UP, the research protocol, inclusion/exclusion criteria, and informed consent will be changed to reflect the possibility of this event reoccurring. During this time, no new participants will be recruited and the research procedures for currently enrolled participants will be stopped. Each UP will be recorded and reported throughout the study.

7.3 REPORTING UNANTICIPATED PROBLEMS TO PARTICIPANTS

Any new information gained during the study that may affect a participant's willingness to continue in the study will be reported to all currently enrolled participants.

8. STATISTICAL CONSIDERATIONS

8.1 SUMMARIZE THE STATISTICAL ANALYSIS STRATEGY FOR EACH SPECIFIC AIM

Descriptive statistics (e.g., frequency, mean, standard deviation, variance, range) will be generated for all study variables. Continuous study variables will also be examined for normality and homogeneity of variances using visual inspection methods (e.g., histograms, box plots, residuals, Normal Q-Q plots) and quantitative methods (Shapiro-Wilk test). If these assumptions are violated, the continuous study variables will be transformed, as necessary (e.g., log transformation). Exploratory analysis of the association between participant characteristics and study outcomes will be tested using Pearson correlation coefficients, chi square, and analysis of variance.

To analyze study aims 1 and 2, multi-level regression models will examine the within-person correlations between TAC and BrAC measurements, including peak TAC/BrAC and area under the TAC/BrAC curves (AUC). Models will test within-person correlations between TAC and BrAC during the in-lab alcohol administration and naturalistic drinking bouts and will investigate whether correlations differ across conditions. Multi-level models will test TAC predicting drinks consumed and the odds and frequency of alcohol-related harms (e.g., hangover, missed classes), and will examine whether BrAC accounts for additional variance in those outcomes. Person-specific algorithms for predicting BrAC from Skyn TAC data will be developed using a backwards step-wise multiple linear regression approach starting with Skyn TAC data as the primary predictor and adding relevant covariates (e.g., fat-free mass, skin temperature) that result in statistically significant and/or clinically meaningful improvements to the model.

To analyze study aim 3, multi-level regression models will be used to assess within-person changes on repeated measures along with between-person individual differences. A linear growth curve model will be used to test the hypothesis that alcohol-specific satiety increases with time and additional drinks. Timepoint (1-6) and drug (alcohol or placebo) will be included in the model as within subject factors. Compared to placebo, alcohol is predicted to be associated with higher rates of change (slope) in satiety. Next, AUDIT will be included as a continuous predictor of slope in the model to test the hypothesis that participants with fewer alcohol dependence symptoms (lower AUDIT scores) report reduced satiety. Finally, subjective craving scores (Alcohol Urge Questionnaire; AUQ) from each timepoint will be included in the model. The effect of satiety over time is expected to remain significant after controlling for craving. Alcohol-specific satiety is expected to be negatively associated with measures of reward and incentive motivation for alcohol (BAES, APT, Dot Probe). Outcomes from each of these measures will be included in separate multi-level models with satiety scores as the primary dependent measure and timepoint (1-6) and drug (alcohol, placebo) as within-subject factors to determine the effect of additional dependent measures on within-person change in alcohol specific-satiety over time (slope).

To analyze aim 4, a repeated measures analysis of variance (ANOVA) will be used to assess the effect of a dietary supplement on alcohol-specific satiety in a 2(alcohol, placebo) x 2(timepoints) design. It is

predicted that compared to placebo, a GLP-1 stimulating dietary supplement will increase alcohol-specific satiety.

To analyze aim 5, linear regression will be used to assess the association between HMGB1 levels as a function of BrAC during the laboratory alcohol sessions. Data processing and analyses will be completed in R and SPSS.

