Breathalyzer measurement of BAC or BrAC requires frequent repeated measures that may be too burdensome and invasive for participants [14-17]. In contrast, TAC sensors provide a mostly passive and non-invasive approach for continuously monitoring alcohol exposure. TAC sensors are worn on the ankle or wrist and measure the 1% of alcohol that is eliminated through the skin via insensible perspiration or sweat [16, 18-21]. One limitation of TAC is that it is not quantitatively equivalent to BAC or BrAC. TAC reflects an individual's relative alcohol exposure, whereas BAC/BrAC reflect absolute alcohol exposure, which provides actionable information about a person's likely level of cognitive and physical impairment due to alcohol use [18, 22]. Unfortunately, there are currently no reliable methods for directly estimating BAC from TAC, due to the variety of factors that can impact individual differences in TAC (e.g., sex, age, fat-free mass, skin temperature) [15, 21-26]. Translating TAC to BAC/BrAC is necessary prior to leveraging wearable TAC sensors to provide actionable knowledge to inform just-in- time harm reduction interventions. The most unobtrusive and user-friendly TAC sensor currently in use is the BACtrack Skyn (Skyn). The Skyn is a small, lightweight wrist-worn sensor that collects TAC data every 20 seconds and that participants are comfortable and willing to wear across extended time periods in natural settings [14-17, 22, 27-30]. The few studies testing the Skyn under controlled laboratory conditions suggest that Skyn TAC values strongly correlate with BrAC [15] and can be used to estimate BAC at low or moderate BAC levels [31]. However, it is often infeasible and unethical to dose participants in laboratory settings to the excessive levels they dose themselves in natural settings. Additionally, laboratory studies preclude examining whether TAC values predict next-day alcohol-related harms, such as hangovers or blackouts. While two studies have compared the Skyn to another commonly-used TAC sensor in natural settings and found moderate-to-strong correlations between the sensors, [27, 30] we are unaware of any studies comparing the Skyn to BAC or BrAC in natural settings or of any studies examining TAC relative to BrAC as a predictor of volume of consumption and alcohol-related harms (e.g., sickness, hangover). As such, it remains unclear whether correlations between Skyn TAC values and BrAC captured in controlled laboratory settings translate to alcohol use in real-world settings or whether TAC values perform similarly to BrAC in predicting next-day alcohol-related harms [17, 22, 27, 31].

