Increasing evidence also suggests that chronic alcohol consumption promotes neuroinflammation. Increases in systemic inflammation due to alcohol consumption are proposed to contribute both to alcohol-related diseases (including liver disease and cancers) and negative affective states in AUD (e.g., pain, stress). Examination of postmortem human brain tissue demonstrates increased proinflammatory signaling molecules in AUD – one such marker being high-mobility group box 1 (HMGB1) [46, 47]. Evidence from both human and animal brain tissue shows that HMGB1 is a key marker of alcohol-induced immune activation [46-51].

Summary

The goal of the proposed study is to collect pilot data on factors which may predict risk for alcohol use disorder through an inter-lab collaboration using data from 2 alcohol drinking laboratory visits and a 7-day remote assessment period. Correlations between Skyn TAC and BrAC will be assessed in an internally valid, controlled laboratory setting and in an ecologically valid natural setting within the same individuals, and to examine correspondence between TAC and BrAC in predicting alcohol consumption and alcohol-related harms among 42 moderate-heavy drinking adults. During laboratory sessions, additional aims related to individual differences in alcohol risk phenotypes will be assessed. Satiety to the effects of alcohol will be assessed using a novel self-report measure of alcohol-specific satiety and a laboratory model of paced drinking, and the effect of a GLP-1 stimulating dietary supplement on alcohol-specific satiety. In addition, individual differences on an inflammatory biomarker, HGMB1 on drinking outcomes will be assessed.

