3. OBJECTIVE AND OUTCOME MEASURES

Aim 1: Identify the correlations between transdermal alcohol concentration (TAC) and breath alcohol concentration (BrAC) in controlled laboratory and natural settings and compare correlations across settings.

- Outcomes measures: BrAC using the BACtrack S80 and TAC readings using the BACtrack Skyn monitor and light-based finger monitor during laboratory alcohol drinking sessions and a remote assessment period.

Aim 2: Compare TAC and BrAC as predictors of self-reported number of drinks consumed and the odds and frequency of alcohol-related harms in natural settings.

- Outcome measures: BrAC and TAC readings, self-reported number of drinks and alcohol related harms measured using a mobile app questionnaire (LifeData app).

Aim 3: Model individual differences in alcohol-specific satiety using self-report and a paced-drinking alcohol administration laboratory model.

- Outcome measures: Alcohol specific satiety questionnaire, BrAC readings.
- Secondary measures: Self-report alcohol subjective effects (stimulation, sedation, craving), behavioral economic demand for alcohol, attentional bias for alcohol related cues.

Aim 4: Assess the effect of a dietary supplement on satiety to alcohol

- Outcome measures: Blood plasma GLP-1 levels samples during lab sessions via venipuncture before and after supplement administration, alcohol-specific satiety questionnaire

Aim 5: Assess the effect of alcohol exposure on HMBG-1 marker of inflammation

- Outcome measures: Blood plasma levels of HMBG-1 will sampled during lab sessions via fingerprick at timepoints before alcohol administration, 30 minutes after an initial priming drink, and after the final drink.

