8.2 SAMPLE SIZE JUSTIFICATION

An a priori power analysis was conducted using G*Power version 3.1.9.7 (Faul et al., 2007) to determine the minimum sample size required to test the study aims. Results indicated the required sample size to achieve 86% power for detecting a medium effect, at a significance criterion of $\alpha = .05$, was $N = 42$ for within-between interactions on repeated measures.

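### Aim 2 sets out to compare TAC and BrAC as predictors, but the planned analysis names only BrAC added to TAC, which read alone neither ranks them nor shows similar performance

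*Combined protocol and SAP*

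**What the plan says.** Section 3 words the aim as a comparison: "Compare TAC and BrAC as predictors of self-reported number of drinks consumed", together with the odds and frequency of alcohol-related harms in natural settings. Section 2.2 gives the motivation. It says it is unclear "whether TAC values perform similarly to BrAC in predicting next-day alcohol-related harms", and its summary describes the goal as to "examine correspondence between TAC and BrAC in predicting alcohol consumption and alcohol-related harms among 42 moderate-heavy drinking adults".

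The Aim 2 analysis is in Section 8.1 and has two steps. First, "Multi-level models will test TAC predicting drinks consumed and the odds and frequency of alcohol-related harms". Second, the same models "will examine whether BrAC accounts for additional variance in those outcomes". The other Aim 1 and 2 analyses there concern the correlation of TAC with BrAC and the prediction of BrAC from TAC. They do not concern how well each predicts drinks or harms.

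Section 8.2 states "the required sample size to achieve 86% power for detecting a medium effect" as 42 participants, for a within-between interaction on repeated measures. That calculation does not address the Aim 2 comparison.

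**The concern.** The aim, the background and the summary all ask about relative performance. The named analysis asks whether BrAC adds to TAC. These are different questions when the two predictors are correlated, because each one's increment depends on what is already in the model.

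A significant BrAC increment would say that BrAC carries information beyond TAC. It would not say whether TAC carries information beyond BrAC, or which does better alone. A non-significant increment could be taken to mean that TAC suffices, although no margin for similar performance is set and BrAC's own performance would not have been reported.

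The two measures are also collected differently (Section 4.3). The wrist sensor records every 20 seconds. Breath readings are prompted every 20 minutes, until at most one hour after the bout, and are entered by the participant. Missing data may therefore differ between them, and Section 8.1 does not say that the models will use the same bouts.

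**Working it through.** **The plan's own figure.** Section 8.2 does not give the number of groups, the number of measurements or the correlation among them, so its 86% power at N = 42 cannot be reproduced from stated inputs. With λ = f²Nm/(1−ρ), df1 = (k−1)(m−1), df2 = (N−k)(m−1), and assumed f = 0.25 and ρ = 0.5, a layout of k = 6 groups by m = 5 measurements gives 85.9%. Other layouts with k = 2, 3, 4 or 6 and m = 2 to 7 give 62.6% to 99.9%. The figure is attainable and is not in dispute here.

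**Inputs for the Aim 2 check.** Let a = r(outcome, TAC), b = r(outcome, BrAC) and c = r(TAC, BrAC). The documents give none of these, so all values are assumptions. The algebra is for ordinary linear regression, and multi-level, odds and count models will follow it only approximately.

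**Both increments.** R²(joint) = (a² + b² − 2abc)/(1 − c²). BrAC given TAC is R²(joint) − a², and TAC given BrAC is R²(joint) − b². With a = 0.5 and b = 0.6:

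| c | R²(joint) | BrAC given TAC | TAC given BrAC |
|---|---|---|---|
| 0.5 | 0.31/0.75 = 0.4133 | 0.1633 | 0.0533 |
| 0.7 | 0.19/0.51 = 0.3725 | 0.1225 | 0.0125 |
| 0.8 | 0.13/0.36 = 0.3611 | 0.1111 | 0.0011 |
| 0.9 | 0.07/0.19 = 0.3684 | 0.1184 | 0.0084 |

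Swapping a and b swaps the last two columns. TAC's increment reaches zero at c = a/b = 0.5/0.6 = 0.83, so values of c near 0.8 show the sharpest contrast and c = 0.5 a milder one.

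**The same BrAC increment under three rankings.** Fix c = 0.7 and a BrAC increment of 0.05. Then b = ac + √(0.05 × 0.51) = 0.7a + 0.160.
- TAC worse: a = 0.30, b = 0.37 (R² 0.090 against 0.137).
- Equal: a = b = 0.160/0.3, about 0.53 (R² about 0.28 each).
- TAC better: a = 0.70, b = 0.65 (R² 0.49 against 0.42).

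The increment alone is identical in all three.

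**Significance of the increment** (1-df noncentral F, bouts treated as independent).
- 126 bouts, c = 0.5: BrAC's increment is significant with probability 92% when TAC is better (0.6 against 0.5), 98% when they are equal (0.5 each) and over 99% when TAC is worse (0.5 against 0.6).
- 42 bouts, c = 0.7: the test misses a truly worse TAC (0.5 against 0.6) about 20% of the time. When both are 0.5 and each adds information, it is significant only 35% of the time.

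**Precision of a direct contrast** (test for dependent correlations, c = 0.7, independent bouts). With both correlations at 0.5, the 95% half-width for the Fisher-z difference is 0.27, 0.19 and 0.15 for 42, 84 and 126 bouts. Power to separate 0.6 from 0.5 is 17%, 30% and 43%.

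**The case against.** A reader might infer that the plan can never rank the two measures, or that it produces only one of the two increments. The documents do not support that.
- A model containing both predictors is needed to test BrAC's increment. Its TAC coefficient is TAC's effect adjusted for BrAC, and in a linear model the test of that coefficient is the test of TAC added to BrAC.
- BrAC's own correlation can be recovered in a linear model on common bouts if BrAC's coefficient is positive, from the TAC-only result, the TAC-BrAC correlation and the increment: b = ac + √(increment × (1 − c²)) = 0.4 + √(0.1111 × 0.36) = 0.6. The three rankings above would likewise be told apart once the TAC-only fit is read beside the increment.

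This stands, and it limits the point to what the increment shows when read alone and to what the plan commits to report. It does not close the gap. The adjusted TAC effect is not named as a result, the back-calculation is not exact for odds and counts, and it gives no interval for the difference.

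It can also be said that the chosen direction suits the rationale. Section 2.2 presents breath testing as burdensome and TAC as largely passive, so what BrAC adds is the natural question for a substitute. If BrAC's true increment were exactly zero, TAC would be at least as good, because R²(joint) = R²(TAC) ≥ R²(BrAC). That is correct, but a non-significant test does not establish a zero increment, and the stated aim is to compare.

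Finally, Section 8.1 is a short strategy for a pilot, and a direct contrast would be imprecise. That argues for estimation with intervals, not for leaving the contrast out.

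**Conclusion.** The point holds as a gap between the aim and the named analysis that is cheap to close. Section 8.1 names TAC models and one increment. Read alone, that increment does not rank TAC and BrAC, and a non-significant one does not show similar performance. The plan does not commit to reporting TAC adjusted for BrAC, and it names no BrAC-only model, no direct contrast and no common set of bouts.

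That one increment does not determine the ranking is algebraic and does not depend on a particular correlation. The sizes do depend on assumptions. At outcome correlations of 0.5 and 0.6, the two increments are 0.163 and 0.053 at a TAC-BrAC correlation of 0.5, and 0.111 and 0.001 at 0.8. The power figures further assume independent bouts, and the bout counts are not from the documents. Nothing here shows that the sample size is wrong or that the data could not answer Aim 2.

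**What to change.** For each Aim 2 outcome and exposure metric (peak and AUC), fit four multi-level models on the same bouts, limited to those with both measures: covariates only, TAC only, BrAC only, and both. Report:
- BrAC's increment given TAC and TAC's increment given BrAC;
- the difference in fit between the TAC-only and BrAC-only models (AIC or marginal R²), with a bootstrap interval that resamples participants;
- the number of bouts excluded because one measure was missing.

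Present the comparison as estimation. If a conclusion of similar performance is intended, state in advance the margin that would count as similar.

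No new data are needed. The TAC-only and joint models are already implied, so the addition is at most two models per outcome and metric. With three outcomes (drinks, odds of harm, frequency of harm) and two metrics, that is at most 2 × 3 × 2 = 12 extra models. The downside is the loss of bouts that lack one of the measures.
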